## AMENDMENTS

The following amendments and/or administrative changes have been made to this protocol since the last submission.

Amendment number	Date of amendment	Protocol version number	Type of amendment	Summary of amendment
1	07-Mar-2016	2.0	Substantial amendment	
 
Updated contact details
 
Addition of Safety follow-up visits to schedule of events, for 6 months after the last study dose.
 
Removal of Autoantibody collection from Schedule of Events
 
Statistical section has been redrafted for clarity
 
Correction of grammatical, formatting/ spelling errors
 
Addition of Safety follow-up visits in Sections 6.8: patient follow up, 6.11.3 Reporting requirements and 6.12.1.3 Events of Clinical Interest for 6 months after the last study dose.
 

	07-Jun-2016	2.0a	Non substantial amendment	
 
Stool sample instead of rectal swab
 
Correction of formatting and grammatical errors
 

2	30-Jan-2017	3.0	Substantial amendment	
 
Updated contact details
 
Correction of formatting and grammatical errors throughout
 
Eligibility: Updated Performance Status criterion
 
Clarified procedure for pre-registration screening
 
Eligibility: Amended requirements for obtaining PD-L1 status from archival tissue or a new biopsy if archival tissue is unavailable
 
Clarified patients with both PD-L1 positive and negative tumours are eligible. Patients who have had systemic therapy since the biopsy do not need to have a repeat biopsy.
 
Added that a newly obtained biopsy is mandatory at baseline (prior to Cycle 1/Day 1) for the assignment of PD-L1 status if an archival biopsy is not available and/or PD-L1 testing on the archival tissue is unsuccessful (see section 4.1 for more details).
 
Added slides of fresh cut sections from Formaldehyde Fixed Paraffin Embedded (FFPE) tissue block will
 

Amendment number	Date of amendment	Protocol version number	Type of amendment	Summary of amendment
				
be assessed by the site Pathologist for PD-L1 testing
 
 
Added if the PD-L1 status has already been obtained from a nationally recognised and MSD-approved laboratory, this will be acceptable and repeat PD-L1 staining will not be required
 
Added if a patient has had a repeat biopsy for the purpose of PD-L1 staining for the PePS2 trial but the biopsy failed to yield sufficient cells for PD-L1 status, this patient will still be eligible to enter the PePS2 trial but will be categorised as PD-L1 non-evaluable.
 
Added clearer definition of performance status of 2 in the inclusion and exclusion criteria.
 
Added flow chart of Treatment Assessments
 
Clarified assessments performed up to 28 and 7 days before treatment
 
Clarified procedure for registration
 
Added table for frequency of sample collection
 
Investigator brochure changed to Summary of Product Characteristics
 
Added another Event of Clinical interest and reference to immune-mediated AEs
 
Statistical considerations re-written and dose reduction removed.
 

5	14-Jun-2017	4.0	Substantial amendment	
 
Clarified trial objectives, outcomes measures and exclusion criteria in trial synopsis
 
Timing of some of the screening and week 0 assessments changed.
 
Additional measurements for cortisol and CRP added plus smoking history.
 
Clarified amount of time blood pressure and ECG to be performed.
 
To routine laboratory tests table added CRP and cortisol measurements and amended urinalysis.
 
Abbreviations table updated
 
Background and Rationale updated
 

Amendment number	Date of amendment	Protocol version number	Type of amendment	Summary of amendment
				
 
Updated objectives and outcome measures, clarifying and summarising primary objectives and secondary and exploratory outcome measures
 
Updated Trial Design
 
Amended Inclusion and Exclusion criteria
 
Amended Patient Registration to receive a copy of the ICF
 
Treatment assessments updated to reflect changes in addition of and time when samples collected.
 
Updated Dose Modification and Toxicity Management section
 
Changed prohibited concomitant medications so that systemic steroids can be taken by patients have started trial treatment but steroids can only be taken for a maximum of 2 weeks
 
Added patients who meet RECIST criteria for progressive disease (PD) may be continued on trial treatment if the treatment is tolerable and believed to be of clinical benefit to Patient Withdrawal section.
 
During reporting period, only details of all treatment-related AEs will be documented.
 
Amended Dose Modification and toxicity management section
 
Amended pembrolizumab Infusion Reaction Dose modification and Treatment Guidelines table
 
Amended Statistical Considerations section
 

6	14 th August 2017	5.0	Substantial amendment	
 
Updated contact details
 
Specified instructions for collection and freezing of stool sample.
 
Correction of formatting errors
 

7	10-Jul-2018	6.0	Substantial amendment	
 
Trial contact details updated.
 
Table 4 updated.
 
Section 15: Regulatory framework updated.
 
Section 16: Updated to include General Data Protection Regulations.
 
Minor spelling and formatting changes throughout.
 

## TRIAL SYNOPSIS

### Title

PePS2: A phase II trial of pembrolizumab in patients with non-small cell lung cancer and a performance status of 2

### Trial Design

Multi-centre, single-arm phase II trial, testing pembrolizumab in a population of patients with non-small cell lung cancer (NSCLC) and an Eastern Cooperative Oncology Group (ECOG) performance status of 2

### Trial Objectives

This is a phase II trial of programmed cell death protein 1 (PD-1) blockade in patients with programmed death ligand 1 (PD-L1) defined NSCLC and an ECOG performance status of 2 with the primary purposes:

- To determine that pembrolizumab is safe and tolerable at the selected dose
- To detect the durable clinical benefit in this population of patients treated with pembrolizumab that would justify further investigation

### Secondary objective:

- To measure patient health related quality of life (HRQoL)

### Exploratory objective:

- To discover possible biomarkers to predict for a response to pembrolizumab

### Outcome Measures

#### Primary outcome measures:

- Toxicity defined as the occurrence of a treatment-related dose delay or treatment discontinuation due to an adverse event
- Durable Clinical Benefit defined as the occurrence of a complete response (CR), partial response (PR) or stable disease (SD) without prior progressive disease (PD) at or after the second scheduled CT scan (scheduled to occur at 18 weeks).

#### Secondary outcome measures:

- Objective Response (OR)
- Progression-free survival time (PFS)
- Time to Progression (TTP)
- Overall survival time (OS)
- Health related quality of life (HRQoL)
- Duration of objective response (DOR) and duration of stable disease (DSD)

### Patient Population

Patients with non-small cell lung cancer and an ECOG performance status of 2 (Appendix 1)

### Sample Size

60 patients

### Inclusion Criteria (not exhaustive - refer to section 4)

- Histologically confirmed PD-L1 status defined NSCLC.
- ECOG performance status 2 with no deterioration over the previous 2 weeks assessed by consenting physician.

- Patients must be ambulatory and capable of all self-care but unable to carry out any work activities
- Patients must be up and about more than 50% of waking hours
- Life expectancy > 12 weeks.
- Uni-dimensionally measurable disease according to Response Evaluation Criteria in Solid Tumours (RECIST) v1.1 (Appendix 2).
- Computerised Tomography (CT) scan of chest and abdomen within 28 days of starting pembrolizumab.
- Adequate haematological function:
  - Platelet count  $\geq 100 \times 10^9 / L$
  - Neutrophils  $\geq 1.5 \times 10^9 / L$
  - Haemoglobin  $\geq 90 \text{ g/L}$
- Adequate hepatic function:
  - Serum bilirubin  $\leq 1.5 \times$  upper limit of normal (ULN)
  - Serum transaminases  $\leq 2.5 \times$  ULN
- Adequate renal function
  - Creatinine clearance  $< 1.5$  times ULN concurrent with creatinine clearance  $> 50 \text{ ml/min}$  (calculated by Cockcroft and Gault equation – see Appendix 3). If this is  $\leq 50 \text{ ml/min}$  then an isotopic Glomerular Filtration Rate (GFR) may be carried out and must be  $> 50 \text{ ml/min}$
- Provision of signed and dated, written informed consent prior to any trial specific procedures, sampling and analyses.

#### **Exclusion Criteria (not exhaustive - refer to section 4)**

- Patients who do not meet the criteria of performance status = 2 on the ECOG Performance scale (Appendix 1), i.e. patients should not be:-
  - ambulatory and able to carry out work of a light or sedentary nature e.g. light house work, office work.
- Untreated symptomatic brain or leptomeningeal metastatic disease.
- Medical or psychiatric conditions comprising informed consent.
- Any medical condition which in the opinion of the Investigator would compromise the ability of the patient to participate in the trial or which would jeopardise compliance with the protocol.
- Radiotherapy within 28 days of trial treatment.
- Active autoimmune disease that has required systemic treatment in past 2 years.
- Chronic usage of steroids or other immunosuppressant medication.
- Previous history of pneumonitis.
- Any evidence of clinical autoimmunity.

#### **Trial Duration**

4 years (1 year recruitment, 2 years trial treatment, 1 year patient follow up)

## Trial Schema

**Table 1: Schedule of Events**

	Screening		Treatment											Follow up		
	Within 28 days of entry	Within 7 days of treatment	Week/Cycle (21 Days ± 3 days)											Cycle 11-35 (21 Days ± 3 Days)	End of treatment	30 day Follow up
Week (approximate)			0	3	6	9	12	15	18	21	24	27	N			
Cycle			1	2	3	4	5	6	7	8	9	10	N			
Informed consent 	X															
Demographics / Medical History/Prior Medications 	X															
Charlson Index 		X														
HRQoL Questionnaire 			X	X	X	X	X	X	X	X	X	X	X	X		
Vital Signs 		X	X	X	X	X	X	X	X	X	X	X	X	X	X	
Physical Examination		X		X	X	X	X	X	X	X	X	X	X	X	X	
ECOG performance status 	X	X	X	X	X	X	X	X	X	X	X	X	X	X	X	
12-Lead ECG 	X															
Review Adverse Events and Concomitant Medications 		X	X	X	X	X	X	X	X	X	X	X	X	X	X*	X*
Full blood count (FBC) 		X		X	X	X	X	X	X	X	X	X	X	X	X	
Comprehensive serum chemistry panel 		X		X	X	X	X	X	X	X	X	X	X	X	X	
Urinalysis 		X			X			X			X	X*	X	X	X	
Coagulation parameters 	X														X	

	Screening		Treatment											Follow up		
	Within 28 days of entry	Within 7 days of treatment	Week/Cycle (21 Days ± 3 days)											Cycle 11-35 (21 Days ± 3 Days)	End of treatment	30 day Follow up
Week (approximate)			0	3	6	9	12	15	18	21	24	27	N			
Cycle			1	2	3	4	5	6	7	8	9	10	N			
HIV, Hepatitis B and C 	X															
Pregnancy Test – Urine or Serum β-HCG 		X														
Renal function – GFR 		X														
Thyroid function and cortisol 		X		X		X		X		X		X	X 	X	X	
PBMC sample (60 ml blood) 			X	X	X (10ml)	X			X (10ml)				X (10ml)		X	
Stool sample 			X													
Cytokine/Chemokine Panel and proteomics 			X			X			X			X		X		
Germline DNA 			X													
ctDNA 			X			X			X			X		X		
Tumour Imaging with contrast 	X				X			X			X		X 		X 	X 
Study drug administration (30 minute infusion)			X	X	X	X	X	X	X	X	X	X				
Tumour biopsy (if archived tissue not available) 	X															

	Screening		Treatment											Follow up		
	Within 28 days of entry	Within 7 days of treatment	Week/Cycle (21 Days ± 3 days)											Cycle 11-35 (21 Days ± 3 Days)	End of treatment	30 day Follow up
Week (approximate)			0	3	6	9	12	15	18	21	24	27	N			
Cycle			1	2	3	4	5	6	7	8	9	10	N			
Optional tumour biopsy from patients with durable clinical benefit post therapy 														X		
Survival assessment 																X

1.	Written informed consent must be obtained prior to performing any protocol specific procedure and within 28 days to starting treatment. Patient will need to be re-consented to PePS2 if over 28 days to treatment start.
2.	Includes smoking history, history of treatment for the primary diagnosis, including prior systemic, radiation treatment and surgical treatment, and best response to prior systemic treatments. Date of last prior cancer treatment must be documented.
3.	For Charlson Index see Appendix 4.
4.	QoL questionnaires include Functional Assessment of Cancer Therapy – Lung (FACT-L) questionnaire, EQ- 5D and patient generated subjective global assessment questionnaires, see Appendix 5. To be carried out prior to treatment.
5.	Vital signs to include: temperature, pulse, respiratory rate and blood pressure (average of 3 BP readings).
6.	For ECOG performance status criteria see Appendix 1.
7.	A standard 12-lead ECG will be performed, in triplicate if clinically abnormal rhythm detected, using local standard procedures once at screening. Clinically significant abnormal findings should be recorded as it should be reported as a concurrent condition. Additional time points may be performed as clinically necessary.
8.	Adverse Events (AEs) and laboratory safety measurements will be graded per NCI Common Terminology Criteria for Adverse Events (CTCAE) version 4.0, Appendix 6. All adverse experiences, whether gradable by CTCAE or not, will also be evaluated for seriousness. *In addition to AE and Concomitant Medication review at each cycle, extra safety monitoring will be performed after the last trial dose monthly for up to 6 months.
9.	Routine laboratory tests (e.g., Full blood count (FBC); comprehensive serum chemistry panel; urinalysis) will be performed by the local trial site laboratory or their contract laboratory. Following cycle 13, urinalysis should be performed every 9 weeks*. FBC, serum chemistry and urinalysis may be collected up to 48 hours prior to any Cycle "X", Day 1 dosing. Routine laboratory tests (serum chemistry; haematology) for screening should be performed within 7 days of first treatment.
10.	Prothrombin (PT) / International Normalised Ratio (INR) and partial thromboplastin (aPTT) should be collected at Screening and at the mandatory Safety Follow-up Visit after discontinuation of trial therapy. Coagulation parameters should be determined throughout the trial when clinically indicated.
11.	Testing will be performed by the local laboratory at Screening. Include Hepatitis C Virus (HCV) RNA (qualitative), Hepatitis B surface Antigen (HBsAg), and Human Immunodeficiency Virus (HIV) 1/2 antibodies.
12.	For women of reproductive potential, a urine pregnancy test will be performed within 72 hours of the first dose. If urine pregnancy results cannot be confirmed as negative, a serum pregnancy test will be required. See Section 4.3 (Contraception).
13.	Patients must have adequate renal function as defined by Creatinine clearance $<1.5 \times \text{ULN}$ concurrent with creatinine clearance $>50 \text{ ml/min}$ (calculated by Cockcroft and Gault equation – see Appendix 3, or as per institutional standard). If this is $\leq 50 \text{ ml/min}$ then an

	isotopic GFR may be performed and must be $\geq 50$ ml/min.
14.	Analysis of cortisol, T3, T4 and TSH (Thyroid Stimulating Hormone) will be performed by the local site laboratory. Following Cycle 2, testing will be performed every other cycle.
15.	60 ml blood collected before the start of infusion at cycle 1, cycle 2, cycle 4 and on termination of treatment and 10ml blood collected before the start of infusion at cycle 3, 7 and 10. Processing and storage of blood samples are to be carried out as described in the PePS2 Laboratory Manual.
16.	Collected before start of infusion 1. Processing and storage of the stool samples are to be carried out as described in Section 7.6.3.
17.	Collected before start of infusion at cycles 1, 4, 7, and 10. Processing and storage of blood samples are to be carried out as described in PePS2 Laboratory Manual. Analysis will be performed by a central laboratory.
18.	Collected before start of infusion at cycle 1. Analysis will be performed by a central laboratory. Informed consent for future biomedical research samples must be obtained before the DNA sample. DNA sample for analysis should be obtained predose, on Day 1 (or with the next scheduled blood draw). This sample should only be taken once from each subject.
19.	Collected before start of infusion at cycles 1, 4, 7, 10 and 13 and on termination of treatment. Analysis will be performed by a central laboratory. Processing and storage of blood samples are to be carried out as described in PePS2 Laboratory Manual.
20.	
Tumour imaging by CT with contrast will be performed within 28 days prior to enrolment. The same imaging technique has to be used in a patient throughout the trial. Scans will be reported by RECIST 1.1 (Appendix 2).
 
Tumour imaging will be performed every 9 weeks whilst the patient remains on trial therapy. CT scan results must be ready prior to cycle 4, 7, 10 etc. to allow the treating clinician to make decision about treatment continuation.
 
Follow up CT scans will only be required every 9 weeks until progression or until commencement of another cancer treatment for patients who come off treatment due to toxicity. Response status will be assessed by the trial site.

21.	
A newly obtained biopsy is mandatory during screening (prior to cycle 1/day 1) for the assignment of PD-L1 status if an archival biopsy is not available and/or PD-L1 testing on the archival tissue is unsuccessful (see sections 4.1 and 5.2.1.1 for more details).
 
The biopsy may be either Endobronchial ultrasound (EBUS) or Computer-Tomography (CT)-guided. Refer to the PePS2 Laboratory Manual re: PD-L1 testing.

22.	One optional newly obtained biopsy for patients who were initially responsive but have relapsed on treatment may be taken at the end of treatment. The biopsy may be either Endobronchial ultrasound (EBUS) or Computer-Tomography (CT)-guided. Specific instructions for tissue collection and shipment are provided in the PePS2 Laboratory Manual.
23.	Follow up will be completed every 4 weeks for 6 months then every 12 weeks to record treatment after progression and death date.

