### 7.9.2 Prohibited Concomitant Medications

Subjects are prohibited from receiving the following therapies during the Screening and Treatment Phase (including retreatment for post-complete response relapse) of this trial:

- Anti-cancer systemic chemotherapy or biological therapy within 28 days prior to the first dose of trial treatment and while participating in the trial.
- Immunotherapy not specified in this protocol.
- Chemotherapy not specified in this protocol.
- Investigational agents other than pembrolizumab.
- Radiation therapy
  - **Note:** Radiation therapy to a symptomatic solitary lesion or to the brain may be allowed after consultation with the Trials Office. Recommencement of trial treatment after radiation therapy will be at the discretion of the PI after consultation with the PePS2 Trial Office.
- Live vaccines within 30 days prior to the first dose of trial treatment and while participating in the trial. Examples of live vaccines include, but are not limited to, the following: measles, mumps, rubella, chicken pox, yellow fever, rabies, BCG, and typhoid (oral) vaccine. Seasonal influenza vaccines for injection are generally killed virus vaccines and are allowed; however intranasal influenza vaccines (e.g. Flu-Mist®) are live attenuated vaccines, and are not allowed.
- Glucocorticoids for any purpose other than to modulate symptoms from an event of clinical interest of suspected immunologic etiology. The use of physiologic doses of corticosteroids may be approved after consultation with the PePS2 Trial Office.
- Whilst participating on the trial, patients may be given systemic steroids due to an acute medical situation but the steroids may only be given for a maximum of 2 weeks. During this period, trial treatment must stop and can be restarted when the steroid administration is complete. If the subject requires the continued use of steroid treatment for more than 2 weeks, they should be withdrawn from the trial.
- Any form of immunosuppressive therapy within 7 days prior to the first dose of trial treatment and while participating on the trial. Replacement therapy (e.g. thyroxine, insulin, or physiologic corticosteroid replacement therapy for adrenal or pituitary insufficiency, etc.) is not considered a form of systemic treatment.

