### 7.11 Patient Withdrawal

The Investigator will make every reasonable effort to keep each patient on trial. However, if the Investigator removes a patient from the trial treatment or if (s)he declines further participation final assessments will be performed, if possible. All the results of the evaluations and observations, together with a description of the reasons for trial withdrawal, must be recorded in the CRF. For patients withdrawing from trial treatment for reasons other than withdrawal of consent or due to disease progression then continue with RECIST 1.1 scans until documented progression as per protocol. For patients who have come off treatment due to unacceptable toxicity, CT scans will be performed every 9 weeks until disease progression or until the patient starts another anti-cancer treatment. CT scans are to be reported according to RECIST v1.1 criteria (see Appendix 2).

Following assessment by the Principal Investigator and discussion with the PePS2 Trial Office, patients who meet RECIST criteria for progressive disease (PD) may be continued on trial treatment if the treatment is tolerable and believed to be of clinical benefit. Documentation of continued clinical benefit should be recorded in the patient's medical notes by an Investigator.

In the event of a patient's decision to withdraw from the trial, the Investigator must ascertain from which aspects of the trial the patient wishes to withdraw, and record the details on the Withdrawal CRF. All patients will continue to be followed-up, and all information and tissue samples collected up until the point of withdrawal, will be retained and analysed.

Patients who withdraw from the trial due to AEs (clinical or laboratory) will be treated and followed according to accepted medical practice. All pertinent information concerning the outcome of such treatment must be recorded in the CRF.

The following are justifiable reasons for the Investigator to withdraw a patient from trial:

- Unacceptable toxicity
- Unforeseen events: any event which in the judgement of the Investigator makes further treatment inadvisable
- SAE requiring discontinuation of treatment
- Withdrawal of consent
- Serious violation of the trial protocol (including persistent patient attendance failure and persistent non-compliance)
- Withdrawal by the Investigator for clinical reasons not related to the trial drug treatment

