## 13 STATISTICAL CONSIDERATIONS

### 13.1 Definition and Calculation of Outcome Measures

#### 13.1.1 Primary Outcomes

The trial design is based on two co-primary outcome measures representing toxicity and efficacy. The toxicity co-primary outcome measure for the trial is defined as the occurrence of a treatment-related dose delay or treatment discontinuation due to an adverse event.

Patients will have CT scans every 9 weeks from baseline until disease progression. On each occasion, overall tumour burden will be assessed using RECIST 1.1, according to the study protocol. The efficacy co-primary outcome measure for the trial is durable clinical benefit, defined as the occurrence of a complete response (CR), partial response (PR) or stable disease (SD) without prior progressive disease (PD) at or after the second scheduled CT scan (scheduled to occur at 18 weeks).

For example, a disease response of (CR / PR / SD) at 9 weeks, followed by a disease response of (CR / PR / SD) at 18 weeks would constitute efficacy. Likewise, (CR / PR / SD) at 9 weeks, missing data at 18 weeks, and (CR / PR / SD) at 27 weeks would also constitute efficacy. Patients for whom the primary efficacy outcome could not be determined will be taken as not experiencing durable clinical benefit.

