#### **Frequency of Tumour Re-evaluations**

For the PePS2 trial, clinical response rate, durable clinical benefit (CR+PR+SD $\geq$ 18 weeks), PFS and duration of response will be evaluated radiologically by a CT scan of the chest and abdomen and other clinically relevant areas at baseline and at 9 weekly intervals and by clinical measurement at 3 weekly intervals until progression or discontinuation of trial medication. The final CT scan should be performed within 28 days of discontinuation of trial medication.

For patients who discontinue treatment prior to progression CT scans and clinical measurements should, where possible, continue to be performed in accordance with the relevant schedule of assessments.

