## DCB

Patients are scheduled to have CT scans every 9 weeks from baseline until disease progression. On each occasion, overall tumour burden will be assessed using RECIST 1.1, according to the study protocol. DCB is defined as the occurrence of CR, PR or SD without prior PD at or after the second scheduled CT scan. The second scan is scheduled to occur at the end of treatment cycle 6 at 18 weeks. For many reasons, scans often do not take place on the desired date. The exact timing of scans is largely out of the control of the trials office. The third scheduled scan is at 27 weeks. In NSCLC, disease status could easily change during the intervening 9 weeks. When calculating DCB, we include scans that occurred at least 16 weeks after registration.

For example, a disease response of (CR / PR / SD) at the first scheduled scan at 9 weeks, followed by a disease response of (CR / PR / SD) at the second scheduled scan at 16+ weeks would constitute DCB. Likewise, (CR / PR / SD) at 9 weeks, missing data at 18 weeks, and (CR / PR / SD) at the third scheduled scan at 27 weeks would also constitute DCB.

Patients for whom the DCB outcome could not be determined will be taken to be non-responders.

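### Table 1 footnote 20 requires off-treatment CT only after a toxicity stop, contrary to section 7.11: a minor conflict that can bias durable clinical benefit slightly downward

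*Protocol*

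**What the plan says.** Four parts of the protocol govern CT after treatment stops, and they do not agree.

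- **Table 1, footnote 20.** Follow-up scans will only "be required every 9 weeks until progression or until commencement of another cancer treatment", and this applies "for patients who come off treatment due to toxicity".
- **Section 7.11.** "For patients withdrawing from trial treatment for reasons other than withdrawal of consent or due to disease progression then continue with RECIST 1.1 scans", until progression is documented. A separate sentence then covers toxicity stops and ends their scans at progression or new anti-cancer treatment.
- **Sections 2.2.1.2, 2.2.2.1 and 13.1.1.** CT is every 9 weeks from baseline until progression, with no condition about being on treatment. SAP 9.1.1 describes the same schedule.
- **Appendix 2, Frequency of Tumour Re-evaluations.** One paragraph runs scans until progression or the end of trial medication and adds: "The final CT scan should be performed within 28 days of discontinuation of trial medication". The next says that, for patients who stop before progression, scans "should, where possible, continue to be performed in accordance with the relevant schedule of assessments".

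Two scoring rules turn a missing scan into a result. SAP 9.1.1 states: "When calculating DCB, we include scans that occurred at least 16 weeks after registration". Protocol 13.1.1 states: "Patients for whom the primary efficacy outcome could not be determined will be taken as not experiencing durable clinical benefit". SAP 9.1.1 and 9.2.2 repeat the second rule, and SAP 9.2.2.1 confines imputation to covariates.

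**The concern.** Footnote 20 is attached to the schedule of events, the table that site staff are most likely to work from. A site that relies on it has no stated duty to scan a patient who stops for a reason other than toxicity. Such stops are foreseeable. Section 7.11 lists withdrawal by the investigator for clinical reasons unrelated to the drug. Section 7.9.2 says of systemic steroids given for an acute medical situation: "If the subject requires the continued use of steroid treatment for more than 2 weeks, they should be withdrawn from the trial". Because that sentence speaks of leaving the trial and not of leaving treatment, it also invites a site to stop scanning.

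If scanning ends early, a patient whose disease is still controlled can be counted as a DCB failure. DCB is a co-primary outcome, and protocol 13.2.1 makes a separate decision in each of six cohorts, with mean sizes of 6.8 to 13.1 patients in SAP Table 5. Later stops do not touch DCB but do affect the time-to-event outcomes. TTP is censored at the last scan without progression. So are PFS, DOR and DSD if the patient is alive at analysis.

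**Working it through.** The plan gives no figure on this point, so the check is a comparison of texts followed by a sizing under stated assumptions.

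**1. One patient under each rule.** Suppose the last dose is cycle 3 (week 6) and the investigator then stops treatment for a clinical reason unrelated to the drug, without progression. Taking week 6 as the stop, the final CT in Appendix 2 is due by week 6 + 4 = 10.
- Footnote 20: no further scan is required. No scan reaches 16 weeks, so the patient is a DCB failure.
- Section 7.11: scans continue, the 18-week scan is done, and DCB is decided by its result.

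**2. The exposed window.** The earliest scan that counts is at 16 weeks and the final CT comes at most 28 days after stopping, so the cut-off is 16 - 4 = week 12. The 16 weeks run from registration, while Table 1 weeks run from first dose. With a gap of g weeks between the two, the cut-off on the treatment clock is 12 - g. A stop between weeks 12 and 16 may also miss the window if the final CT is done promptly. Stops for confirmed CR need at least 6 months on treatment (section 7.4), so they cannot affect DCB.

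**3. Expected loss.** Lost DCBs = 60 x share exposed x fraction unscanned x DCB rate. The last three inputs are assumptions: 2-5% stop before week 12 without progression for a reason other than toxicity or consent withdrawal; half to all are at sites following footnote 20; the DCB rate is 20-40%.
- Low: 60 x 0.02 x 0.5 x 0.2 = 0.12 (0.2 percentage points of 60).
- High: 60 x 0.05 x 1 x 0.4 = 1.2 (2.0 points).
- At 30% DCB: 60 x 0.02 x 0.5 x 0.3 = 0.18 to 60 x 0.05 x 1 x 0.3 = 0.9 (0.3 to 1.5 points).

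**4. Effect on cohort approval.** Let d be the share of true DCBs lost, so the observed rate is p(1 - d). The assumptions in step 3 give d = 0.02 x 0.5 = 1% to 0.05 x 1 = 5%. The BEBOP rule was simulated with the SAP Table 3 priors, the cohort-size distribution of SAP 9.3.2, n = 60, both approval criteria, 1,500 trials per setting, and the association parameter omitted. The range of approval probability over the six cohorts was:

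| SAP scenario | SAP Table 6 | d = 0 | d = 5% | d = 10% |
|---|---|---|---|---|
| 1 | 0.872-0.903 | 0.879-0.926 | 0.859-0.911 | 0.825-0.889 |
| 9 | 0.737-0.994 | 0.738-0.995 | 0.695-0.992 | 0.641-0.992 |

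The d = 0 values lie up to about 3 points above the SAP's, so only differences between columns should be read. At d = 5%, the top of the assumed range, approval falls by 1.5 to 2.6 points per cohort in scenario 1 and by 0.3 to 4.3 points in scenario 9.

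**5. If exactly one DCB is lost.** A second simulation (efficacy criterion only, 3,000 trials per scenario) recoded one DCB at random as a failure. At least one cohort with true efficacy above 10% then fell below the 0.7 bar in 17.3%, 31.2%, 25.2% and 15.0% of trials in scenarios 1, 5, 8 and 9. These figures are conditional on a whole DCB being lost. Scaling in proportion to the expected loss:
- Scenario 1: 0.18 x 17.3% = 3% to 0.9 x 17.3% = 16%.
- Scenario 5: prevalence-weighted efficacy is 0.364 x 0.10 + 0.398 x 0.15 + 0.238 x 0.30 = 16.75%. The expected loss is 60 x 0.01 x 0.1675 = 0.10 to 60 x 0.05 x 0.1675 = 0.50, and 0.10 x 31.2% = 3% to 0.50 x 31.2% = 16%.

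**The case against.** The strongest reply is that the plan's intent is clear and footnote 20 is simply the outlier. It says when scans are required and forbids none, so a site that follows 7.11 breaches nothing. The outcome definitions in both documents assume scanning to progression. The more natural reading of the second Appendix 2 paragraph is that it covers every stop before progression and that the schedule it mentions is the 9-weekly timing just described. SAP 9.1.1 does not restrict DCB to on-treatment scans, so a routine CT reported by RECIST could still count. Any bias is conservative.

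All of that stands, and it is why the point is minor. A reader might infer that sites are told to do opposite things, or that off-treatment scans are barred; the wording supports neither. A reader might also infer that patients who stop for immune-related events lose their scans. They do not, because footnote 20 covers toxicity stops.

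What remains is that a site reading only the schedule of events would see no duty to scan. Appendix 2 does not fully repair this: its continuation is qualified as far as possible, and the paragraph before it ends scanning with the medication.

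**Conclusion.** The inconsistency is real and minor. Footnote 20 conflicts with 7.11 and with the outcome definitions. Where it is followed, an early stop for a reason other than toxicity or progression can be scored a DCB failure only because no scan was done. The direction is downward. The size is about 0.1 to 1.2 lost DCBs in 60 patients, and it rests wholly on assumed rates of such stops and of sites following the footnote.

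The 15-31% figures in step 5 might tempt a reader to say that up to a third of trials would reach a different decision. The documents do not support that. Those figures presuppose one lost DCB, whereas the expected loss is mostly below one. The scaled range is about 3-16% in scenarios 1 and 5, so usually no cohort decision changes.

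The effect on PFS, TTP, DOR and DSD was not sized. It reaches any non-toxicity stop before progression, including patients who stop in confirmed CR, for whom section 7.4 allows treatment to resume on recurrence although footnote 20 requires no scan to detect it.

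**What to change.** 1. Reword footnote 20 so that 9-weekly CT continues until progression for every patient who stops treatment for a reason other than progression or withdrawal of consent.
2. Decide whether scans end at new anti-cancer therapy, and state that rule identically in footnote 20 and in the general sentence of 7.11. At present the footnote and the toxicity sentence of 7.11 have this end point and the general sentence does not. If scans do end there, a patient who starts chemotherapy before week 16 will still lack a qualifying scan, but by a stated rule.
3. In Appendix 2, remove the clause that ends scanning when trial medication ends, or limit it to stops for progression.
4. In 7.9.2, both in the steroid bullet and in the closing rule on prohibited treatments, say that the patient is withdrawn from trial treatment and that scans continue as in 7.11.

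The cost is one footnote and a few sentences in an amendment, plus a few off-treatment scans that 7.11 already requires.
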